4.1 Inclusion Criteria

Subjects who meet all of the following conditions will be entered into the trial:

(1) Patients aged from 18 to 65 years.

(2) Testing positive for serum hepatitis B surface antigen (HBsAg) for more than 6 months.

(3) Diagnosis of decompensated liver cirrhosis, which was defined as liver cirrhosis with serious complications, such as ascites, hepatic encephalopathy, and esophageal and gastric variceal hemorrhage, according to Prevention and Treatment of Chronic Hepatitis B (China 2009).

(4) Negative pregnancy test (female patients of fertile age).

(5) Volunteering to participate in this clinical trial, and able to understand and provide signed informed consent.

(6) Patients with hepatitis B infection-related cirrhosis treated with anti-HBV therapy.

4.2 Exclusion Criteria

Subjects who meet one of the following conditions will not be allowed to enter the test:

(1) Hepatocellular carcinoma or other malignancies.

(2) Pregnancy or lactation.

(3) Sepsis.

(4) History of HCV infection.

(5) History of HIV infection.

(6) Other liver diseases, including, but not limited to, alcoholic liver disease, non-alcoholic fatty liver disease, drug-induced hepatitis, autoimmune hepatitis, Wilson disease, and hemochromatosis.

(7) ALT or AST \geq 10*ULN.

(8) Creatinine clearance (CLcr) < 50 mL/min (calculated according to the Cockcroft-Gault formula) (Appendix 2).

(9) Diabetes mellitus (HbA1c > 8.5%).

(10) History or family history of mental or neural diseases, especially depression, depressive tendencies, epilepsy, and hysteria.

(11) Severe cardiovascular disease including, but not limited to, uncontrolled hypertension (systolic blood pressure \geq 160 mmHg or diastolic blood pressure \geq 100 mmHg), New York Heart Association (NYHA) cardiac function grade III (Appendix 1) and above, unstable angina pectoris, myocardial infarction, or intracoronary angioplasty occurring within 6 months, QTc interval (QTcF or QTcB) \geq 500 ms, II° or III° atrioventricular block, or other uncontrolled arrhythmias.

(12) Serious diseases of the blood system, including, but not limited to, various anemias and hemophilia.

(13) Serious digestive diseases including, but not limited to, gastrointestinal ulcers and colitis.

(14) Severe respiratory diseases including, but not limited to, pneumonia, pulmonary tuberculosis, chronic obstructive pulmonary disease, and interstitial pulmonary disease.

(15) Allergic constitution or history of severe allergies, especially allergies to stem cell products or ingredients.

(16) History of alcohol or drug abuse within 6 months.

(17) Participation in other clinical trials within 3 months.

(18) Unable or unwilling to provide informed consent or unable to comply with test requirements

(19) Other situations unsuitable to participation in the opinion of the researcher.

4.3 Withdrawal criteria

All participants who meet one of the following criteria would withdraw from the trial:

(1) Subject's request to stop test for lack of efficacy, intolerance, adverse reactions, or withdrawal of informed consent by the participants.

(2) Poor compliance (unable to comply with the requirements of the test).

(3) Pregnancy or lactation for women during treatment.

(4) Any complication, adverse event (AE), or laboratory abnormality occurring during the

treatment, which in the opinion of the investigator, indicates that continued participation in the study is not in the best interest of the subject.

(5) Other conditions unsuitable for continuation of the test in the opinion of the investigator.

If participants withdraw from the study because of the occurrence of AEs or laboratory abnormalities, these important event and test results should be recorded in case report form (CRF).

The causes of shedding cases should be recorded in detail. Data involving safety and efficacy should be obtained as much as possible and all end-of-study assessments should be carried out with the subject's consent. All data should be kept intact for reference.

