3.2.2 Secondary endpoints

(1) Liver function, including the levels of albumin (ALB), prothrombin activity (PTA), total bilirubin (TBIL), and cholinesterase (CHE) during 48 weeks after the first UC-MSC infusion..

(2) Complications, including abdominal infection, gastrointestinal hemorrhage, hepatic encephalopathy, and hepatorenal syndrome during 48 weeks after the first UC-MSC infusion.

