6.13 Visit 8 (75 months ±30 days)

- (1) Survival status: Telephone call;
- (2) Whether liver cancer occurs or not: Telephone call.

6.14 Unplanned visits (when the study requires it or after withdrawal from the trial ahead of time)

If the subject needs additional visits (such as follow-up monitoring of adverse reactions or AEs) or withdraws from the trial ahead of time, the laboratory and auxiliary examinations should be improved as much as possible, recording AEs and the accompanying treatment. The measures taken by the researchers, including the results of laboratory tests, should be recorded in the original medical records and in the planned out-of-plan visit table in the CRF.

7 Efficacy Assessments

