9.6.2 AEs and SAEs after the study

AEs and SAEs after the study refers to any event that occurs outside the visit period of the AE or SAE specified in 9. 3 (method, frequency, and time of discovery of an AE or SAE). Researchers do not have to take the initiative to explore AE and SAE in subjects who had completed clinical studies and interviews. However, if the researcher is aware of any SAE (including death) at any time after a subject has withdrawn from the study, and the event might be related to the MSC, the researcher should promptly notify the unit responsible for the clinical study.

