10.2 Subjects withdraw from the trial

Each participant may, at any time of the study, withdraw from the study for any reason (special or non-special) without being unfairly treated. The subjects who withdraw from the study will not be restricted in their treatment and may continue to receive conventional treatment or other appropriate treatment.

The medical examinations in their screening period should be cancelled for the enrolled patients who fail to be screened into the study, and the reasons for failure should be recorded in the completion/termination page.

If the successfully screened participants withdraw from the clinical trial during the study period, the medical examination for these subjects should be completed at the current visit, and the reasons for quitting the study should be recorded in the completion/termination page.

11 Data Management

This scheme only provides general requirements for data management. Data entry and modification: Data entry and management shall be performed by the data manager of the statistical unit, and will be managed by using an electronic database. To ensure the accuracy of the data, two data administrators are required to input and proofread the data independently.

For questions in the CRF, the data administrator should fill out the question-answer form and ask the researcher. The data administrator will modify, confirm, and enter the data according to the researcher's answers, and can issue the question-answer form again if necessary. The data administrator will import the data into the designated database, hand over the data to the statistician for statistical analysis, and the statistical analysis will write the statistical analysis report.

12 Statistical analysis

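### Survival and HCC follow-up after withdrawal is not secured: section 4.3 withdraws patients from the trial, not only from infusions, and the related sections conflict

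*Protocol*

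**What the plan says.** - **What withdrawal means.** Protocol section 4.3: "All participants who meet one of the following criteria would withdraw from the trial". No section defines a status of off infusions but still in follow-up. Section 10.1 counts a patient as a completer only after all treatments and all visits to Visit 8.
- **A complication as trigger.** Criterion (4) of 4.3 begins "Any complication, adverse event (AE), or laboratory abnormality occurring during the" and is limited to the treatment period and to the investigator's opinion. Section 3.2.2 makes a secondary endpoint of "Complications, including abdominal infection, gastrointestinal hemorrhage, hepatic encephalopathy, and hepatorenal syndrome during 48 weeks after the first UC-MSC infusion". The trial is open label (3.3).
- **At withdrawal.** Section 10.2: "the medical examination for these subjects should be completed at the current visit, and the reasons for quitting the study should be recorded". Section 6.14 says that if a patient "withdraws from the trial ahead of time, the laboratory and auxiliary examinations should be improved as much as possible". It adds AEs and accompanying treatment but names neither survival nor HCC.
- **After withdrawal.** Section 9.6.2 asks for notification "if the researcher is aware of any SAE (including death) at any time after a subject has withdrawn from the study", and only where the event could be linked to the cells.
- **Pointing the other way.** Section 4.3 also says "Data involving safety and efficacy should be obtained as much as possible and all end-of-study assessments should be carried out", with consent. Section 7.1 has patients followed for 75 months. Section 12.3.4 ends follow-up at an endpoint event, death or study end and does not list withdrawal. The same paragraph, however, restricts the analysis to eligible participants who got their allocated treatment and were followed.
- **Source of the primary outcomes.** After week 48 the visit schedule contains only telephone calls on survival and HCC, at months 24, 48, 60 and 75.

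**The concern.** Both primary endpoints, survival and HCC-free survival over 75 months, depend on calls made long after treatment ends. A site that follows 4.3 and 10.2 literally could close a patient's participation in the first weeks and never place those calls. A site that follows 12.3.4 would keep calling. The protocol supports both.

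The choice matters because withdrawal need not be random. A patient withdrawn for a complication of decompensated cirrhosis plausibly has a worse outlook than one who stays, although the protocol gives no figure for this. The judgement is made with the allocation known. If such patients are censored at withdrawal, the Kaplan-Meier and Cox analyses treat them as having the same future risk as those who remain. Where the arms lose different kinds or numbers of patients, the hazard ratio is biased. An analysis plan cannot recover outcomes that were never collected, so this has to be settled in the protocol.

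**Working it through.** **1. The provisions side by side**

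| Section | Supports continued calls? |
|---|---|
| 4.3, lead-in | No: the patient leaves the trial |
| 4.3, closing paragraph | Partly: best effort and end-of-study assessments, no schedule, survival and HCC not named |
| 6.14 | Silent on survival and HCC |
| 9.6.2 | No active search; known, possibly cell-related events only, so of little use for controls, who receive no cells |
| 10.2 | Examination finished at the current visit; calls not mentioned |
| 12.3.4, follow-up rule | Yes: withdrawal is not an end of follow-up |
| 12.3.4, who is analysed | Can exclude those withdrawn |

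These cannot all be followed in the same way, and none states the rule for the calls.

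**2. The plan's own figures (section 12.1)**

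The sentence on rates is garbled. I read it as 60% (control) and 85% (UC-MSC) disease-free at 60 months.

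- Implied hazard ratio: ln(0.85)/ln(0.60) = 0.318.
- Power with 100 per group, two proportions, two-sided 0.05: mean rate 0.725; z = (0.25×√100 − 1.96×√(2×0.725×0.275)) / √(0.60×0.40 + 0.85×0.15) = (2.5 − 1.238)/0.606 = 2.08, so power is 98.1%. The stated bound of over 80% holds.
- Dropout: 100/(1 − 0.20) = 125. The 20% is inferred, since no rate is stated; a 25% add-on, 100×1.25, also gives 125.

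Power is therefore not the issue. With all 125 per group followed for 75 months, about 82 events are expected and power at 0.318 exceeds 99%. What is at stake is bias.

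**3. Illustration with assumed strata**

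Assumptions, none from the protocol: no true effect; each arm has 20% high-risk patients with 60-month survival 20% and 80% others with 70%, so overall 0.20×0.20 + 0.80×0.70 = 60%. A fraction w of the UC-MSC arm, all high-risk, is withdrawn early and censored; no control is.

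Apparent survival S = ((0.20 − w)×0.20 + 0.56)/(1 − w); apparent HR = ln(S)/ln(0.60), a 60-month summary.

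| w | S | HR |
|---|---|---|
| 5% | 0.59/0.95 = 62.1% | 0.93 |
| 10% | 0.58/0.90 = 64.4% | 0.86 |
| 20% | 0.56/0.80 = 70.0% | 0.70 |

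The last row removes every high-risk UC-MSC patient, so it is the extreme of this model.

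**4. A second model**

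The withdrawn fraction has k times the hazard of the rest, overall 60-month survival is held at 60%, and withdrawal is again in the UC-MSC arm only. The rejection rate uses a normal approximation with 125 per arm randomised.

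| w | k | HR | Two-sided rejection rate (nominal 5%) |
|---|---|---|---|
| 10% | 2, 3, 5 | 0.93, 0.88, 0.83 | 7%, 9%, 14% |
| 20% | 2, 3, 5 | 0.86, 0.77, 0.68 | 11%, 21%, 40% |

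**5. Equal withdrawal in both arms**

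With no true effect, identical withdrawal gives identical apparent curves and an HR of 1. At the plan's rates, the second model with the same w and k in both arms moves 0.318 to about 0.31 to 0.29 (w = 10%) or 0.31 to 0.28 (w = 20%). For example, at w = 10% and k = 3: ln(0.871)/ln(0.638) = 0.31.

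**6. If missing outcomes counted as failures**

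Section 12.2 places missing main efficacy data in an unresponsive set. Applied to survival in the step 3 example, UC-MSC survival would be (0.20 − w)×0.20 + 0.56 = 59%, 58% or 56% against 60%. The bias reverses direction, so its sign depends on a rule that the protocol leaves unclear for time-to-event outcomes.

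**The case against.** A reader might infer that withdrawn patients are not followed for survival or HCC and that their later deaths are never observed. The protocol does not say so. Section 12.3.4 does not make withdrawal an end of follow-up. Section 4.3 asks for end-of-study assessments with consent, and since Visit 8 consists only of the survival and HCC calls, that clause can be read to include them. Section 10.2 concerns the medical examination, not the calls. Section 6.14 sets no limit on the number of unplanned visits. Section 9.6 keeps visiting patients with AEs until the event resolves, stabilises or is explained, or the patient is lost.

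Two further inferences also go too far. Not every complication in the 48-week endpoint window triggers withdrawal: criterion (4) covers the treatment period, about 8 weeks, and needs the investigator's judgement. The synopsis version has no such time limit but does not name complications. Nor is there a criterion that can apply to the UC-MSC arm alone: the synopsis clause on being unable to receive the cells goes on to cover failure to follow the protocol generally, and 4.3(2) is neutral between arms.

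The numerical illustrations are constructed, with invented risk strata or hazard multiples and withdrawal in one arm only. Even the most extreme hazard ratios, about 0.7, are far from the planned 0.318.

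All of this stands. It limits the point to follow-up that is not secured. It does not remove the conflict, because best effort without a schedule is not a rule, and the follow-up sentence in 12.3.4 sits beside one that can exclude those withdrawn.

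**Conclusion.** The point holds as a gap and a conflict. The protocol does not separate stopping infusions from leaving follow-up, and sections 4.3, 6.14, 9.6.2, 10.2 and 12.3.4 do not agree on whether survival and HCC are still sought after withdrawal. It does not establish that follow-up stops, or that those withdrawn are the patients most likely to die.

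The size depends on how many are withdrawn, how different they are and whether the arms differ. None of this is given. Under the one-arm assumptions above, 10% withdrawal gives an apparent hazard ratio of about 0.93 to 0.83 with no true effect, and 20% gives about 0.86 to 0.68. Equal withdrawal biases the contrast much less, and counting missing outcomes as failures could reverse the direction. The 20% figure is inferred from the step from 100 to 125 per group. The remedy is cheap and the loss, if it occurs, cannot be repaired in analysis, so the change is worth making.

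**What to change.** Reconcile the synopsis withdrawal criteria and sections 4.3, 6.14, 9.6.2, 10.2 and 12.3.4:

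- Define discontinuation of study infusions separately from withdrawal from follow-up.
- State that a participant in either arm who meets a withdrawal criterion stays in the survival and HCC calls at months 24, 48, 60 and 75, and in the 48-week complication record where willing, unless consent to contact is withdrawn.
- In 12.3.4, remove the condition that can exclude withdrawn participants and analyse them in their randomised arm, as 12.2 already intends.
- Leave the clinical rules for stopping infusions as they are.

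The cost is amendment wording and at most four telephone calls per withdrawn participant, at visits already in the schedule. The small downside is that the follow-up data will include patients who are off their assigned treatment.

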4.4 Termination criteria

The test shall be terminated if the following criteria are met:

(1) Serious safety problems occurred during the test.

(2) Termination requested by the unit responsible for clinical research (such as funding or management reasons).

(3) Termination requested by independent ethics committee or administrative department.

5 Interventions

5.1 Human mesenchymal stem cells

(1) Origin: UC-MSC derived from healthy fetal umbilical cords and processed by pulverization, centrifugation, culture, and activation *in vitro*.

(2) Culture: UC-MSC were prepared in an approved good manufacturing practice (GMP)-compliant facility and identified as described previously. In brief, with the written consent of the maternity patients, fresh human umbilical cords were obtained after birth and collected in cold Xeno-free MesenCult-XF medium (STEMCELL Technologies Inc., Vancouver, Canada). The mesenchymal tissues in the umbilical cord Wharton's jelly were diced into cubes of approximately 0.5 cm^3 and washed with Hanks' balanced saline solution (Gibco Invitrogen, Waltham, MA, USA). Then, the tissue pellets were seeded in a tissue culture flask (Corning Enterprises, Corning, NY, USA) in α -minimal essential medium (MEM) supplemented with 10% fetal bovine serum (STEMCELL Technologies). The medium was replenished every 3 days. The UC-MSC were cultured and collected between the third and fourth passages for infusion.

5.2 Conditions for preparation and monitoring

5.2.1 Umbilical cord collection

(1) Collection materials

- ① Collection bottle (2% gentamicin containing medium, 100 mL).
- 2 Registration form.
- ③ Informed consent form.
- ④ Uniform marker.
- ⑤ Outer packing bag.

(2) Collection requirements

① Collection site

Collection of the umbilical cord should be carried out in the unit designated by the person in charge of the umbilical cord bank. The collection should be carried out strictly under aseptic conditions to prevent contamination with pathogens.

② Collection staff

The collection staff should go through strict education and training before they can collect the umbilical cords.

③ Collection materials

The materials in direct contact with the umbilical cord should comprise sterilized medical or scientific supplies. To prevent contamination with microorganisms, materials that are not in direct contact with the umbilical cord should also comprise disinfected supplies. In addition, to prevent contamination with foreign bodies other than pathogens, the use of materials with dust particles and short fibers should be avoided. Supplies for collection shall be carefully assembled by qualified staff in accordance with SOP and distributed to the collection site in advance.

(3) Collection method

① Collection time

The umbilical cord should be quickly collected after fetal delivery in an aseptic state.

2 Collection before placental delivery

• Within 10 seconds after fetal delivery, clamp the umbilical cord at 5–8 cm near to the fetal navel using hemostatic forceps (to ensure that the fetal navel is intact), avoid contact with other objects as far as possible, and cut the umbilical cord outside of the hemostatic forceps.

- Put the broken end of the umbilical cord into a pre-prepared collection bottle, slide it slowly into the collection bottle, and then cut off the end connected to the placenta. Place the whole umbilical cord in the collection bottle and seal it.
- During collection after natural labor, the umbilical cord should be washed with 2% gentamicin-containing normal saline and loaded into the collection bottle to prevent secondary pollution.

③ Collection after placental delivery

- After fetal delivery, the umbilical cord was cut off from the fetal navel, and the fetus was taken away for normal treatment.
- Rinse umbilical cord with 2% gentamicin-containing normal saline to remove blood and meconium contamination.
- Put the umbilical cord in a pre-prepared collection bottle and seal it.

(4) Transportation requirements

① Transportation staff

The staff responsible for transporting the umbilical cord should be designated by the person in charge and have received strict education and training.

- ② Transportation conditions
- In the course of transportation, the ambient temperature should be 4–8 °C, and the temperature change should not exceed 5 °C.
- To meet the requirements of the transportation temperature, materials with thermal insulation function should be used for the container, and ice cubes should be loaded.
- ③ Transportation materials
- Transportation list.
- Tape.
- Thermal insulation box.
- ④ Transportation procedures
- Check the number of the umbilical cord.
- Check whether the collection bottle and related data are complete.
- Check the markers for accuracy.
- Fill in the number, date, and time on the transportation form, as well as the name of the transportation staff.
- Put ice bags and foam fillers in the thermal insulation box, to reach the required temperature.

- Avoid X-ray irradiation, temperature change, and excessive turbulence during transportation.
- The time from collection to separation shall not exceed 24 hours.

(5) Donator selection criteria

① Maternal requirements

- 36–42 weeks of pregnancy, normal development and nutrition.
- No infectious diseases (e.g., hepatitis B, hepatitis C, AIDS, or syphilis).
- No malignant tumors.
- No serious complications during pregnancy.
- No family history of hereditary diseases.
- 2 Fetal requirements
- No malformations.
- No family history of hereditary diseases.

5.2.2 UC-MSC quality control

For quality control of the UC-MSC, the cultured cells at the third passage were examined for their phenotypes using flow cytometry analysis, for example, high expression of CD44, CD73, CD90, and CD105, but no expression of CD31, CD34, CD45, or HLA-DR. Alternatively, the digested cells were cultured in conditioned medium (STEMCELL Technologies), and subsequently cultured for osteogenesis and adipogenesis differentiation assays. Briefly, the digested cells were cultured in osteogenesis-inducing medium (Gibco Invitrogen) consisting of MesenCult basal medium, osteogenic stimulatory supplements, dexamethasone, β -glycerophosphate, and ascorbic acid ions for five weeks, or in adipogenic induction medium (Gibco Invitrogen) consisting of MesenCult basal medium and MesenCult adipogenic stimulatory supplements for two weeks. Subsequently, osteogenesis was assessed using alkaline phosphatase staining, and adipogenesis was assessed using oil red O staining. Moreover, the UC-MSC were confirmed as negative for all the tested contaminants before infusion, including *Mycoplasma* spp., gram-positive and gram-negative bacteria, and fungi. The endotoxin levels were below 5 EU/kg and viability was > 80%.

